5.1 General Study Design and Plan

This is an Open-Label Extension (OLE), multicentre study to evaluate the long-term safety, tolerability and efficacy of EDP1815 in participants with mild, moderate and severe atopic dermatitis. Participants who have completed the 16-week treatment period in the EDP1815-207 parent study may be eligible to enrol in this study.

The doses administered in this study are the same as those administered in the EDP1815-207 parent study and are as follows:

- Group 1: 1.6×10^{11} total cells of EDP1815 administered as 2 capsules once daily
- Group 2: 6.4×10^{11} total cells of EDP1815 administered as 2 capsules once daily
- Group 3: 8.0×10^{10} total cells of EDP1815 administered as 1 capsule once daily

[figure not shown]
No placebo will be administered in this study. The following will apply for all EDP1815-207 participants who transition into this study:

- EDP1815-207 Cohort 1 participants will receive 1.6×10^{11} total cells of EDP1815 in EDP1815-208 (Group 1)
- EDP1815-207 Cohort 2 participants will receive 6.4×10^{11} total cells of EDP1815 in EDP1815-208 (Group 2)
- EDP1815-207 Cohort 3 participants will be randomized 1:1 to receive either 1.6×10^{11} total cells of EDP1815 (Group 1), or 6.4×10^{11} total cells of EDP1815 (Group 2) in EDP1815-208
- EDP1815-207 Cohort 4 participants will receive 8.0×10^{10} total cells of EDP1815 in EDP1815-208 (Group 3)

The total number of participants will be dependent on the number of participants who elect and are eligible to participate in the OLE study following participation in the EDP1815-207 parent study.

The total duration of participation in this study is up to a maximum of 40 weeks from Day -1 to follow-up. As shown in Figure 1, participants will undergo a Day -1 visit, a 36-week treatment period consisting of 6 study visits and a 4-week post-treatment follow-up visit.

Figure 1: Study Schema

5.2 Randomisation and Blinding

This is an OLE study with all participants taking EDP1815 capsules and as such no blinding is required for the study medication in this study. Participants in Cohort 3 in the EDP1815-207 parent study that are eligible for this study will be randomized 1:1 to receive either 1.6×10^{11} total cells of EDP1815, or 6.4×10^{11} total cells of EDP1815.

Investigators and participants will continue to be blinded to the participant's treatment assignment in the EDP1815-207 parent study to minimize bias.

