4.7. Rationale for study design and selection of dose

4.7.1. Dose Rationale

The doses, and corresponding regimen selected for evaluation within this study are:

- Group 1: 1.6×10^{11} total cells of EDP1815 administered as 2 capsules once daily.
- Group 2: 6.4×10^{11} total cells of EDP1815 administered as 2 capsules once daily.
- Group 3: 8.0×10^{10} total cells of EDP1815 administered as 1 capsule once daily.

The doses administered in this study are the same as those administered in the EDP1815-207 parent study.

No placebo will be administered in this study. The following will apply for all EDP1815-207 participants who transition into this study:

- EDP1815-207 Cohort 1 participants will receive 1.6×10^{11} total cells of EDP1815 in EDP1815-208 (Group 1)
- EDP1815-207 Cohort 2 participants will receive 6.4×10^{11} total cells of EDP1815 in EDP1815-208 (Group 2)
- EDP1815-207 Cohort 3 participants will be randomized 1:1 to receive either 1.6×10^{11} total cells of EDP1815 (Group 1), or 6.4×10^{11} total cells of EDP1815 (Group 2) in EDP1815-208
- EDP1815-207 Cohort 4 participants will receive 8.0×10^{10} total cells of EDP1815 in EDP1815-208 (Group 3)

The pharmacological site of action of EDP1815 is within the epithelium of the small intestine where EDP1815 interacts with immune and epithelial cells. These interactions modify the systemic immune system and promote inflammation resolution throughout the body. The preclinical and clinical data generated to date suggest this is a broad effect working across Th1, Th2 and Th17 pathologies. As the intent is to generate a maximal inflammation-resolving phenotype regardless of inflammation pathology, the dose response is expected to be common across indications, and therefore we aim to cross-compare to previous studies to support this hypothesis.

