7.7 Visit Windows

All data will be reported according to nominal visits. For example, if a Week 4 visit occurred on Day 30 instead of the nominally expected Day 28 it will be reported and included in the summary statistics/statistical analyses for Week 4.

Scheduled visits which occur outside the protocol-specified visit window (e.g., if the Week 4 visit occurred on Day 32, outside of the Day 25-31 window), this will be noted as a protocol deviation but data collected will still be included in all summary and analysis tables.

Unscheduled visits and Early Termination visit will not be included in summary or analysis tables, unless they are baseline measurements or provide data towards a safety endpoint which looks at worst-case post-baseline.

All listings will include all collected data even if they are from an unscheduled visit.

8 Summary of Study Data

All continuous variables will be summarized using the following descriptive statistics: n (non-missing sample size), mean, SD, median, maximum, and minimum. The frequency and percentages (based on the non-missing sample size) of observed levels will be reported for all categorical measures.

In general, all data will be listed, sorted by group (1, 2, and 3), country, site number and participant number. Relevant listings will include whether the assessment was performed and the date, study day/visit and time of the assessment as applicable.

Any study population or safety tables, listings or figures that display treatment will always present the actual treatment received rather than the planned treatment as the primary objective is to evaluate the safety of EDP1815. For efficacy summaries planned treatment will be used.

Unless otherwise specified below, all summary tables will be structured with a column for each group (groups 1 and 2 will be presented in 207 cohorts 1-3 delivery and group 3 will be presented in 207 cohort 4 delivery) and an additional 'Total' column which contains all patients included in the relevant interim or final analysis.

The labels presented for each group will be as follows:

- Group 1 = 1.6×10^{11} TCPD
- Group 2 = 6.4×10^{11} TCPD
- Group 3 = 8.0×10^{10} TCPD

For summaries of safety endpoints that look at the period defined since first dose of active IMP either in this study or the relevant parent study, the data will be ordered and labelled as follows:

- 1.6×10^{11} TCPD (For 207 cohorts 1-3 delivery only)
- 6.4×10^{11} TCPD (For 207 cohorts 1-3 delivery only)

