- 6.4×10^{11} TCPD to 1.6×10^{11} TCPD (For 207 cohorts 1-3 delivery only)
- 8.0×10^{10} TCPD (For 207 cohort 4 delivery only)
- Total

For efficacy outputs, columns will be ordered and labelled as follows:

- For 207 cohorts 1-3 delivery:
 - 1.6×10^{11} TCPD in this study, Placebo in the parent study
 - 1.6×10^{11} TCPD in this study, 1.6×10^{11} TCPD in the parent study
 - 1.6×10^{11} TCPD in this study, 6.4×10^{11} TCPD in the parent study
 - 6.4×10^{11} TCPD in this study, Placebo in parent study
 - 6.4×10^{11} TCPD in this study, 6.4×10^{11} TCPD in the parent study
 - Total
- For 207 cohort 4 delivery:
 - 8.0×10^{10} TCPD in this study, Placebo in the parent study
 - 8.0×10^{10} TCPD in this study, 8.0×10^{10} TCPD in the parent study
 - Total

For the analysis:

- For study disposition summaries where it is appropriate to report information on participants that have failed screening, the enrolled population will be used.
- For the primary estimands around adverse events, together with estimands based on efficacy count endpoints looking into the use of rescue medications, the FAS will be used along with DPS1 and DPS2.
- For the responder efficacy endpoints the FAS along with DPS4b will be used
- For supplementary estimands for the key efficacy responder endpoints the FAS along with DPS4 and DPS4a will be used.
- For continuous endpoints the FAS along with DPS4a will be used.
- For safety endpoints where data is collected at specific timepoints the FAS along with DPS3 and DPS4 will be used.

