9.1 Early Stopping

In the event that the study is stopped early and only a reduced amount of outputs are needed, safety data will only be reported for the period beginning with the first dose of active IMP in this study. Only incidence and number of events will be presented for the following categories:

- TEAEs
- Serious TEAEs

Data will be presented as collected, no imputations or data exclusion will be made.

The list of outputs produced in the case the study is stopped early are provided in 16Appendix 1: List of Tables, Figures and Listings.

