9.2.1 Estimands

The primary safety estimands will use the FAS or the parent study specific FAS for the study/cohort specific analysis.

Treatment condition: actual treatment received will be considered.

Population summary measure of interest:

- For the endpoints looking at the period defined by this study only - the incidence and rate per 100 patient-years of each category of TEAEs (DPS1)
- For the endpoints looking at the period defined since first dose of the active IMP in this study and the relevant parent study - the rate per 100 patient-years of each category of TEAEs by treatment group (DPS2)

Intercurrent events will be accounted for in the following manner:

Table 1: Intercurrent Event Strategies of the Primary Estimand

Discontinuation of treatment	The use of prohibited medications or TCS/TCI rescue therapy, non-compliance with study drug, and any deviations from protocol
Composite strategy Only events which start within 30 days after discontinuation of treatment (TEAEs) will be included in the assessments of incidences and rates	Treatment policy strategy: Data will be used as collected

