16.3 Safety

If the study is stopped early, safety outputs will be produced as planned originally.

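### Does the plan need an output that shows the two randomised arms of Cohort 3 side by side?

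*SAP*

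**What the plan says.** Allocation within 208 is described consistently. Protocol 4.7.1 states that "EDP1815-207 Cohort 3 participants will be randomized 1:1 to receive either" the Group 1 or the Group 2 dose. SAP 5.1 repeats this, and SAP 5.2 says "Participants in Cohort 3 in the EDP1815-207 parent study that are eligible for this study will be randomized 1:1 to receive either" one of the same two doses. Cohort 1 goes to Group 1, Cohort 2 to Group 2 and Cohort 4 to Group 3, without randomisation.

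The displays are organised by dose. In SAP Section 8, unless otherwise specified, "all summary tables will be structured with a column for each group", with a Total. Study population and safety outputs "will always present the actual treatment received rather than the planned treatment", and SAP 9.2.1 repeats this for the primary estimand: "Treatment condition: actual treatment received will be considered". Safety since first active dose uses the active dose across both studies. For efficacy, Section 8 says "For efficacy outputs, columns will be ordered and labelled as follows", followed by combinations of 208 dose and parent dose. No table, figure or listing in SAP Appendix 1 is restricted to Cohort 3.

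The objectives (Protocol 2.1 to 2.3, SAP 4.1) are long-term safety, efficacy, time to onset and biomarkers. Protocol 11.1 and 11.4 and SAP 7.2 rule out inferential testing. Table 9 in SAP Section 14 records that the study was terminated early, that efficacy outputs will not be produced, and that the safety package is reduced.

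**The concern.** A trial that randomises a subset through its IRT would normally be expected to show the randomised comparison somewhere. Here each arm of Cohort 3 is merged with a cohort whose dose was fixed: Cohort 1 in Group 1, Cohort 2 in Group 2. The adverse event overview then puts Group 1 next to Group 2, and a reader may take the gap as a dose effect. If Cohorts 1 and 2 differed in background risk, a gap would appear with no dose effect at all, while the contrast protected by randomisation within 208 stays hidden. At stake would be a misread dose comparison that one extra table could have prevented.

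**Working it through.** **1. Which participants fall in which column.** Inputs: the allocation in SAP 5.1 and the column lists in SAP Section 8. The documents do not state Cohort 3's parent dose. I assume from the column labels that its active dose was 6.4×10^11 and that Cohorts 1 to 3 each had placebo participants.

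| Layout (Cohorts 1–3 delivery) | Column | Cohorts |
|---|---|---|
| 208 only | Group 1 | 1 + 3 |
| | Group 2 | 2 + 3 |
| Since first active dose | 1.6×10^11 | 1 + 3 (parent placebo) |
| | 6.4×10^11 | 2 + 3 |
| | 6.4×10^11, then 1.6×10^11 | 3 only |
| Efficacy (208 / parent) | 1.6×10^11 / placebo | 1 + 3 |
| | 1.6×10^11 / 1.6×10^11 | 1 only |
| | 1.6×10^11 / 6.4×10^11 | 3 only |
| | 6.4×10^11 / placebo | 2 + 3 |
| | 6.4×10^11 / 6.4×10^11 | 2 + 3 |

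Of 10 columns, 7 are mixed, 2 hold only the parent-active part of one Cohort 3 arm, and 1 holds Cohort 1 only. No layout shows both randomised arms. The factual part of the concern is confirmed; the Group 1 and Group 2 rows need no assumption.

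**2. Which columns survive early termination.** SAP 16.2 drops the efficacy tables and figures (5 columns). SAP 16.3.1 lists 28 adverse event tables (14 on DPS1, 14 on DPS2) and 10 laboratory, ECG and vital-sign tables, 38 in all. Four are marked for the early stop, all on DPS1; none of the 14 DPS2 tables is kept (3 columns). This leaves 10 − 5 − 3 = 2 columns, Group 1 and Group 2. SAP 9.1 narrows the primary safety content further: "Only incidence and number of events will be presented for the following categories", namely TEAEs and serious TEAEs.

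**3. How far pooling could mislead.** Cohort sizes are not given. Let Cohorts 1 and 2 each have N participants and Cohort 3 have rN, split equally. The randomised share of each group is f = (rN/2)/(N + rN/2) = r/(2 + r). With no dose effect, Group 1 minus Group 2 has expectation (1 − f)(p1 − p2), where p1 and p2 are the incidences in Cohorts 1 and 2. Take p1 − p2 = 10 points, an invented figure:

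- r = 0.5: f = 0.5/2.5 = 20%; shift = 0.80 × 10 = 8.0 points
- r = 1: f = 1/3 = 33%; shift = 0.667 × 10 = 6.7 points
- r = 2: f = 2/4 = 50%; shift = 0.50 × 10 = 5.0 points

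**4. What a Cohort 3 table could show.** With equal incidence p and n per arm, the Newcombe 95% half-width is √[(p − l)² + (u − p)²], where l and u are the Wilson limits for one arm. For n = 10 and p = 0.2, l = 0.057 and u = 0.510, so the half-width is √(0.143² + 0.310²) = 0.341. Over p = 0.2 to 0.5 (assumed):

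- n = 10: 34.1 to 37.3 points
- n = 20: 24.7 to 28.4 points
- n = 40: 17.6 to 20.9 points

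For the shift in step 3 to reach even the smallest of these, 17.6 points, the background difference would have to be 17.6/0.80 = 22.0, 17.6/0.667 = 26.4 or 17.6/0.50 = 35.2 points for r = 0.5, 1 or 2. Nothing in the documents points to a difference of that size.

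**5. What the plan claims from the columns.** It makes no between-group estimate or test. Protocol 11.3.1 and 11.3.2 define the groups by dose, disclose that two parent dosing schedules are pooled, state the assumption of similarity, and allow separate analysis if parent results contradict it.

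**6. Whether the plan blocks a Cohort 3 display.** It does not. SAP 7.1.1.3 and 7.4.2 allow analysis sets for a specific parent cohort, and 9.2.1, Section 10 and Section 11 carry a cohort-specific FAS into the primary, efficacy and safety analyses. Group 1 and Group 2 columns within a Cohort 3 set would be the two randomised arms.

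**The case for a change.** The best argument for acting is that the display is cheap and adjacent columns invite a dose reading. Protocol 4.7.1 discusses an expected common dose response and comparison with earlier studies. Groups 1 and 2 also differ in manufacturing process (Protocol 6.1), which the sponsor is evaluating in the parent study. The cohort-specific route is optional and nothing is scheduled under it. A shift from pooling does not shrink as numbers grow, whereas sampling error does, and the pooled contrast has sampling error of its own.

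Part of this stands. Group 1 versus Group 2 should not be read as a comparison randomised within 208, and no scheduled output supplies one. But 4.7.1 is a rationale for choosing doses, not an objective. The manufacturing difference weakens the remedy too: Cohort 3's arms carry the same difference and are open-label, so their contrast is not a pure dose effect either. Nor do the documents say how participants entered Cohorts 1 to 3 of the parent study, so the supposed imbalance between Cohorts 1 and 2 is conjecture.

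A separate loose end is that SAP 16.3 says "If the study is stopped early, safety outputs will be produced as planned originally", while 9.1, 11.1 and the Early Stop column cut them. The opening of Appendix 1 makes the Early Stop column govern, and Table 9 confirms the reduction. That sentence is leftover wording and does not bear on how Cohort 3 is displayed.

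**Conclusion.** The concern does not hold. Cohort 3's randomised arms are not shown side by side, but the plan never sets out to compare doses, and its descriptive summaries by dose are valid for a safety extension. After early termination the issue is confined to two columns of a reduced safety package. There, a hypothetical shift of 5.0 to 8.0 points would be set against a contrast with a half-width of about 18 to 37 points. Those figures rest on assumed cohort sizes (Cohort 3 at 0.5 to 2 times the others), an assumed 10-point background difference, 10 to 40 participants per arm and incidences of 20% to 50%. The full column count also rests on the inferred parent dose and placebo participants. The conclusion itself does not depend on them: it follows from the objectives, the descriptive design, and the cohort-specific analysis that the SAP already permits. An extra Cohort 3 table would be a matter of preference, not a correction.

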5.3 Derived variables

5.3.1 General

5.3.1.1 Relative Day

The relative day of an assessment since the start of 208 study will be calculated as:

- For measurement performed on or after the date of first dose in this study:
Date of assessment – date of start of treatment + 1
- For measurements performed before the date of first dose in this study:
Date of assessment – date of start of treatment

The relative day of an assessment since the first dose of active IMP (in this or parent study) will be calculated as:

- For measurement performed on or after the first dose of active IMP:
Date of assessment – date of the first dose of active IMP + 1
- For measurements performed before the first dose of active IMP:
Date of assessment – date of the first dose of active IMP

5.3.1.2 Baseline

The last non-missing value collected before first study dose in the parent study will be taken as the baseline measurement for all parameters. If data is collected on Day 1 of the parent study it will be assumed to be pre-dose regardless of an associated time.

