Secondary endpoints: The Eczema Area and Severity Index (EASI) Score will be utilized to measure the efficacy of EDP1815 in the treatment of atopic dermatitis. In addition to EASI, the Investigator's Global Assessment (IGA), percentage of Body Surface Area (BSA), Product of the IGA and BSA (IGA*BSA), the SCORing Atopic Dermatitis (SCORAD), the Dermatology Life Quality Index (DLQI), the Peak Pruritus Numerical Rating Scale (PP-NRS), the Sleep Disturbance Numerical Rating Scale (SD-NRS), the Patient Oriented Eczema Measure (POEM) and the Atopic Dermatitis Control Tool (ADCT) will be measured throughout the study.

The number of courses of treatment with rescue therapies; and with antibiotic treatment due to skin infection, per participant, will also be measured.

Brief Study Design: This is an Open-Label Extension (OLE) study to evaluate the long-term safety, tolerability, and efficacy of EDP1815 in participants with mild, moderate, and severe atopic dermatitis who have completed the treatment period of a prior clinical study ("parent study") with EDP1815. The parent study of this open label extension protocol is the EDP1815-207 study; A Phase 2, Multicenter, Double-Blind, Placebo-Controlled, Multiple-Cohort Study Investigating the Effect of EDP1815 in Participants for the Treatment of Mild, Moderate and Severe Atopic Dermatitis. The EDP1815-207 study will be referenced as the parent study throughout the protocol.

This study may serve as an open label extension study for future EDP1815 studies in Atopic Dermatitis.

All participants in this study will be treated with EDP1815, regardless of the treatment assignment in the EDP1815-207 study. To minimize bias, during dosing in EDP1815-208, investigators and participants will continue to be blinded to participants' treatment allocation in the parent study whilst it is ongoing. Participants in this study will be treated with EDP1815 for up to 36 weeks, followed by a follow-up visit at approximately 4 weeks after the end of treatment.

Interim safety and efficacy analyses may be performed throughout the study as required for ongoing evaluation of the benefit-risk profile for EDP1815. These may include either all participants enrolled in the study or use of a subset of participants who transitioned to this study from a specific parent study. Interim analyses may also incorporate data collected within the parent Atopic Dermatitis EDP1815 studies which feed into this study.

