Study Duration: The maximum study duration is up to 40 weeks for all participants, which will include a 36-week treatment period and a 4-week post treatment follow-up period. The participants may move directly from the parent study into the open label treatment phase without a break in study treatment, or within 7 days of completing the treatment period of the parent study. If the participants move directly into this study without a break in treatment from the parent study, the Day -1 visit should be performed at the same time as the end of treatment visit of the parent study.

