11.1. General Statistical Considerations

Statistical analysis will be performed using SAS software Version 9.3 or later.

Continuous variables will be summarized using the mean, standard deviation, median, minimum value, and maximum value. Categorical variables will be summarized using frequency counts and percentages.

No inferential statistical testing will be performed. Data will be displayed using summary statistics together with 95% confidence intervals where applicable.

Descriptive statistics will also be used extensively in figures to visualize the data. These include but are not limited to mean (SE) plots against time, waterfall plots for individual changes at a specific time point, vertical bar plots showing percentages of participants meeting a specific criterion, scatter plots to look at correlations between endpoints or timepoints.

Data will be listed in data listings.

Baseline will be defined as the baseline value taken from the parent study. In some cases, change prior to first dose of EDP1815 and change since first dose in this study may also be analyzed.

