7.1.2 Defined Data Point Sets

7.1.2.1 Data Point Set 1 (DPS1)

DPS1 consists of all observed data collected following the first dose of IMP in this study until 30 days after the last dose of IMP.

Note, baseline data will be taken from the parent study.

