7.1.2.3 Data Point Set 3 (DPS3)

DPS3 consists of all observed data collected at a scheduled visit in this study.

Note, changes from baseline will be derived using baseline data from the parent study.

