11.6 Clinical Laboratory Evaluations

Central laboratory data will be used for all safety laboratory evaluations. Table 11 shows the parameters which will be collected and the units in which they will be supplied. Lab data will be transformed as appropriate to the International System of Units (SI units) as part of the SDTM programming and SI units will be used for all summaries.

Haematology and chemistry parameters will be summarized by visit, including change from baseline for all post-baseline visits, using DPS3.

The number and percentage of participants showing shifts from baseline to worst-case post-baseline with respect to the normal ranges will also be summarized for each haematology and chemistry parameter, using DPS1. Categories will be:

- Low
- Normal
- High

Haematology and chemistry values will also be flagged for potentially clinically important (PCI) values if they meet any of the criteria for Grade 2 or higher events according to CTCAE V5.0. The PCI criteria are listed in Table 11. The number and percentage of participants showing shifts from baseline to worst-case baseline with respect to PCI criteria will be summarized for all parameters where PCI criteria have been defined, using DPS1. Categories will be:

- Low
- Within range
- High

For both the normal range and PCI summaries, the determination of worst-case post-baseline will consider both scheduled and unscheduled assessments which occur after the first dose of study treatment. Percentages will use the number of participants with at least one post-baseline assessment available as the denominator. If the baseline value is missing it will be assumed to be normal/within range. Worst-case can be either High or Low and if a participant has post-baseline values both above and below the normal range/PCI criteria then they will be counted in both relevant categories.

Haematology and chemistry data will be listed, including changes from baseline, normal ranges, flags for measurements outside the normal range, and flags for meeting PCI criteria. In addition, for participants who meet at least one PCI criteria, all values within the laboratory type (haematology or chemistry) will be listed separately.

Urinalysis data will be listed only.

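### Full safety outputs measure laboratory, ECG and vital-sign change from the pre-207 value for everyone, so for parent-placebo participants 16 to 17 drug-free weeks fall under a 208 dose label

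*SAP*

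**What the plan says.** SAP 5.3.1.2 defines baseline once, for efficacy and safety alike: "The last non-missing value collected before first study dose in the parent study will be taken as the baseline measurement for all parameters". It does not ask whether that parent dose was active or placebo. The two data point sets behind the 208 safety tables repeat the rule. DPS1 states "Note, baseline data will be taken from the parent study", and DPS3 states "Note, changes from baseline will be derived using baseline data from the parent study".

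SAP 11.6 and 11.7 then use DPS3 for by-visit changes in laboratory, ECG and vital-sign values. They use DPS1 for worst-case shifts; for laboratory values, "The number and percentage of participants showing shifts from baseline to worst-case post-baseline with respect to the normal ranges will also be summarized", and a parallel table applies the potentially clinically important (PCI) criteria. Worst-case values are taken only after the first study dose. By default (SAP section 8) the columns are the 208 dose groups plus a total, with no split by parent treatment.

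Protocol 11.1 also takes baseline from the parent study, but adds: "In some cases, change prior to first dose of EDP1815 and change since first dose in this study may also be analyzed". The SAP plans no such analysis for safety.

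**The concern.** The Protocol Summary says "All participants in this study will be treated with EDP1815, regardless of the treatment assignment in the EDP1815-207 study". A participant who had placebo in 207 therefore meets EDP1815 for the first time on 208 Day 1, and the last drug-free value is the one at Day -1. Protocol Table 4-1 schedules laboratory tests, ECG and vital signs at that visit, or lets the same-day 207 end-of-treatment assessments stand in, so the value exists.

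Measured from the pre-207 value, an abnormality that arose on placebo and persisted appears as a shift under an EDP1815 dose. A value that improved on placebo and worsened on EDP1815 may show no change. Because the 208 columns pool parent-placebo with parent-active participants, a reader of the tables cannot see which mechanism is at work.

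The SAP also handles this differently elsewhere. It anchors one of its two relative-day definitions (5.3.1.1), active exposure (5.3.4.1) and DPS2 (7.1.2.2) to the first active dose. Baseline is not anchored that way.

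**Working it through.** **1. Timeline.** SAP 5.1 gives the parent treatment period: "Participants who have completed the 16-week treatment period in the EDP1815-207 parent study may be eligible to enrol in this study". The 208 treatment period is 36 weeks. 16 + 36 = 52 weeks = 364 days, which matches the top combined-exposure category in SAP 11.2. The Day -1 visit takes place on the same day as the final 207 treatment visit "or within 7 days of completing the treatment period of the parent study", so the gap g is 0 to 1 week.

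**2. Pre-drug share of the interval for a parent-placebo participant.** At 208 week w the share is (16 + g) / (16 + g + w).

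| 208 week | g = 0 | g = 1 |
|---|---|---|
| 4 | 16/20 = 80.0% | 17/21 = 81.0% |
| 8 | 16/24 = 66.7% | 17/25 = 68.0% |
| 16 | 16/32 = 50.0% | 17/33 = 51.5% |
| 24 | 16/40 = 40.0% | 17/41 = 41.5% |
| 36 | 16/52 = 30.8% | 17/53 = 32.1% |

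For parent-active participants the pre-207 value already precedes all drug, so nothing is misplaced.

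**3. Individual flags.** SAP Table 11 flags haemoglobin below 100 g/L or a fall of at least 20 g/L from baseline. Two constructed parent-placebo cases (g/L):

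| Pre-207 | Day -1 | On EDP1815 | Change from pre-207 | Change from Day -1 |
|---|---|---|---|---|
| 140 | 121 | 118 | -22, flagged | -3, not flagged |
| 125 | 140 | 119 | -6, not flagged | -21, would be flagged |

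The QTcF criterion of an increase above 60 ms works the same way. The ALT, AST, bilirubin and creatinine rules use a multiple of the upper limit of normal (ULN) if baseline did not exceed it, and a multiple of baseline otherwise. If ALT was above ULN before 207 and normal at Day -1, the threshold stays at 3 × the old raised value, which is higher than 3 × ULN, and a rise on drug can be missed. Absolute limits (systolic or diastolic pressure, QTcF above 500 ms, white cells, platelets, neutrophils, lymphocytes, sodium, potassium) flag the same post-dose values under either baseline. For these, only the baseline row of the shift table can move.

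**4. Column means.** Let f be the parent-placebo share of a 208 column and d the mean change over the placebo phase. Relative to a last-pre-drug baseline, the column's mean change is off by f × d. The documents give neither. Assuming f = 25% to 50% gives 0.25d to 0.5d. For an assumed d of -3 g/L, that is -0.75 to -1.5 g/L.

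**5. Flag rates with no drug effect.** This is a simulation of 400,000 parent-placebo participants with seven post-dose visits. Half the within-person variance is independent noise and half is autocorrelated at 0.95 per week. Drift occurs only during the placebo phase and persists. SDs, autocorrelation and drift are all assumptions. Each cell gives the percentage with any haemoglobin fall of at least 20 g/L, pre-207 baseline vs Day -1 baseline.

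| Placebo-phase drift | SD 5 g/L | SD 7 g/L | SD 9 g/L |
|---|---|---|---|
| None | 0.8 vs 0.5 | 7.5 vs 5.7 | 18.3 vs 15.8 |
| Fall of 3 g/L | 2.9 vs 0.5 | 13.9 vs 5.7 | 26.7 vs 15.9 |
| Rise of 3 g/L | 0.2 vs 0.5 | 3.6 vs 5.9 | 11.7 vs 15.8 |

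For a QTcF rise of 60 ms or more with 5 ms upward drift, the rates are 0.2% vs 0.03% (SD 12 ms) and 5.3% vs 2.3% (SD 18 ms). In a pooled column these differences shrink by f. At SD 7 with a 3 g/L fall, 13.92 - 5.73 = 8.19 points becomes about 2.0 points at f = 25% and 4.1 at f = 50%.

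**The case against.** The strongest reply is that this hardly matters now. SAP Table 9 records early termination and a reduced output set. SAP 11.1 confines early-stop safety reporting to TEAEs. In Appendix 1 the Early Stop column is negative for every laboratory, ECG and vital-sign table and listing. That stands: if only that package is issued, no affected table appears. It does not close the point, because the opening line of SAP 16.3 says safety outputs are kept in full on early stopping.

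Second, the parent baseline is the Protocol's own definition, and the alternative in Protocol 11.1 is optional. That also stands. A reader might infer that the SAP contradicts the Protocol; it does not. It leaves an option unused where the option would help.

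Third, a reader might infer that the primary safety result is biased. The documents do not support that. The primary endpoints are TEAE incidence and rate, which are not computed from this baseline, and the combined-period rates already start at the first active dose. Under Protocol 9.10, clinically significant laboratory, ECG and vital-sign findings become AEs on the investigator's judgement. The affected tables are secondary and descriptive.

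Fourth, no net bias is shown. With exchangeable visits and no drift the two baselines give the same expected flag rate, and the no-drift row above differs only modestly. The haemoglobin cases show what can happen, not how often.

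Fifth, simply replacing the baseline would average changes of about 20 weeks (parent-active) and about 4 weeks (parent-placebo) in one column at 208 Week 4. This is a fair objection, and it is why the columns must be split.

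**Conclusion.** The point holds for secondary safety outputs wherever the full set is run, interim or final. For parent-placebo participants, by-visit changes and baseline-dependent flags include 16 to 17 weeks before any EDP1815: four fifths of the interval at Week 4, just under a third at Week 36. Changes can be misplaced in either direction. The size in any table rests on the placebo-phase drift, the within-person variability and the parent-placebo share, none of which is documented. The simulated rates are therefore a range under assumptions, not an estimate for this trial.

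It would go too far to move everyone to 208 Day -1: parent-active participants are already on drug then, and the pre-207 value is right for them. Nor do the documents show that any reported table is wrong. Efficacy needs no matching change, because its columns already separate parent placebo and its tables show 207 Week 16 beside the 208 visits.

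**What to change.** In SAP 5.3.1.2, with matching wording in 11.6 and 11.7, do one of the following:

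- define the safety baseline as the last non-missing value before the first dose of active EDP1815, which is the parent baseline for participants on active drug in 207, and the 208 Day -1 value (or the same-day 207 end-of-treatment value) for those on placebo; or
- keep the parent baseline and add change and shift from Day -1 for parent-placebo participants.

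In either case, split the 208 laboratory, ECG and vital-sign columns by parent treatment (placebo or active), so that baselines of different age are not averaged. Keep the parent baseline for efficacy.

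Separately, reconcile the opening line of SAP 16.3 with the Early Stop column and SAP 11.1, so that it is clear whether these tables will be produced at all.

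The cost is one derived baseline flag or one supplementary set of tables, a footnote for the second baseline definition, and extra columns with smaller counts. No new data are needed. The split uses parent allocation, which SAP 7.4.7 makes available from the parent database lock.
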